## 3. Study Procedures:

- Diagnosis, Medical Review, and Prescription of Therapy (Screening, Day -3 to Day -1):
  - Subject will provide electronic informed consent via the EDC portal.
  - Medical Information
    - a. Study staff will review prior and concomitant medications, including over-the-counter medications and supplements.
    - b. Investigator will review the Subject's records during the screening process, looking at inclusion/exclusion criteria, gathering data on vital signs, EKG recordings, and oxygen saturation. These values will be used to compare to values obtained throughout the study. If any contraindication to participation is found, the study drugs will not be provided and the subject will be deemed a screen failure.
  - Diagnosis of COVID-19 will be confirmed
    - a. May be based on PCR testing results, rapid antigen testing results, or clinical presentation at screening as assessed by the Principal Investigator including symptoms such as:
      - Fever
      - Cough
      - Anosmia
  - Subject will be provided a daily diary for recording symptoms.
  - Subject will be randomized into Arm 1 or Arm 2
  - Prescription of treatment drugs
    - a. Arm 1: Medications will be prescribed for Quintuple Therapy
      - Hydroxychloroquine 200MG BID for 10 days, Azithromycin 500mg on day 1, 250mg day 2-5, Vitamin C 3000mg for 10 days, then 1500mg for 20 days, Vitamin D 3000IU for 10 days, then 1500IU for 20 days, and zinc 50mg for 10 days, then 25mg for 20 days.
    - b. Arm 2: Placebos and supplements will be provided (to ensure nutritional parity)
      - Placebo for Hydroxychloroquine BID for 10 days, Placebo for Azithromycin to be taken 2 the on Day 1, then 1 on Days 2-5, Vitamin C 3000mg for 10 days, then 1500mg for 20 days, Vitamin D 3000IU for 10 days, then 1500IU for 20 days, and zinc 50mg for 10 days, then 25mg for 20 days.
    - c. Drugs shall be taken first thing in the morning as soon as the patient has eaten. Vitamins will be taken with lunch and dinner, and then the evening dose of drugs will be right before bed.
  - Monitoring equipment provided
    - a. Home EKG recording device

- b. Pulse Oximeter
    - c. Thermometer
    - d. Urine Pregnancy test if applicable
  - Subject will be isolated as an outpatient
    - a. All CDC recommendations regarding self-quarantine must be followed
- Treatment Period
  - Day 1 following positive test (isolation)

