    - a. Subject will be video called to ensure they have all study materials and go over:
      - Use of home health equipment
        - Subject will take baseline measurements at this time and record it in the diary
      - Diary and how to transmit its contents
      - Medication dosing
    - b. Subject will take pregnancy test if applicable
    - c. Subject will use provided equipment to measure vital signs
      - EKG
      - Oxygen Saturation
      - Temperature
    - d. Subject will take prescribed regimen

Drug	AM Dose	PM Dose
Hydroxychloroquine (or Placebo)	200mg	200mg
Azithromycin (or Placebo)	500mg	---
Vitamin C	1500mg	1500mg
Vitamin D	1500IU	1500IU
Zinc	25mg	25mg

- Hydroxychloroquine and azithromycin will be taken early in the morning with breakfast and right before bed. Vitamins and Zinc will be taken with lunch and dinner
  - Day 2
    - a. Subject will complete AM and PM diaries
    - b. Subject will use provided equipment to measure vital signs
      - EKG
      - Oxygen saturation
      - Temperature
    - c. Subject will take prescribed regimen

Drug	AM Dose	PM Dose
Hydroxychloroquine (or Placebo)	200mg	200mg
Azithromycin (or Placebo)	250mg	---
Vitamin C	1500mg	1500mg
Vitamin D	1500IU	1500IU
Zinc	25mg	25mg

- Day 3
    - a. Subject will be called
      - Ask if they are experiencing any difficulties with swab collection
      - Ask about AE/SAE
      - Update list of prior and concomitant medications
      - Ask about symptom resolution or progression

- Instruct how to collect nasal or oropharyngeal swabs
  - Subject will collect first nasal or oropharyngeal swab
- Answer any questions the Subject may have
- b. Subject will complete AM/PM diaries
- c. Subject will use provided equipment to collect vital signs
  - EKG
  - Oxygen saturation
  - Temperature
- d. Subject will take prescribed regimen

Drug	AM Dose	PM Dose
Hydroxychloroquine (or Placebo)	200mg	200mg
Azithromycin (or Placebo)	250mg	---
Vitamin C	1500mg	1500mg
Vitamin D	1500IU	1500IU
Zinc	25mg	25mg

○ Day 4

- a. Subject will complete AM/PM diaries
- b. Subject will use provided equipment to collect vital signs
  - EKG
  - Oxygen saturation
  - Temperature
- c. Subject will take prescribed regimen

Drug	AM Dose	PM Dose
Hydroxychloroquine (or Placebo)	200mg	200mg
Azithromycin (or Placebo)	250mg	---
Vitamin C	1500mg	1500mg
Vitamin D	1500IU	1500IU
Zinc	25mg	25mg

○ Day 5

- a. Subject will complete AM/PM diaries
- b. Subject will be called
  - remind them to collect swab

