## **6. Schedule of Events**

On next page

Assessment	Screening (Day -7 to Day 1)	Day 1	Day 2	Day 3	Day 4	Day 5	Day 6	Day 7	Day 8	Day 9	Day 10	Day 11	Day 12	Day 13	Day 14	Days 15-30	Month 1 (± 4 days)	Month 2 (± 4 days)	Month 3 (± 4 days)
Informed Consent & Demographics	X																		
Make list of prior and concomitant medications	X			X				X			X				X		X	X	X
Confirmation of COVID-19 diagnosis	X																		
Review of Medical Records	X																		
Prescription of Antimicrobials a	X																		
Provide home health equipment b	X																		
Pregnancy test c		X																	X
Call Subject at home d		X		X		X		X			X				X				
Vitals at home e		X	X	X	X	X	X	X	X	X	X								
Subject will complete AM/PM diary		X	X	X	X	X	X	X	X	X	X	X	X	X	X	X			
Hydroxychloroquine 200mg BID (or placebo)		X	X	X	X	X	X	X	X	X	X								
Azithromycin 500mg (2 tablets) once daily (or placebo)		X																	
Azithromycin 250mg (1 tablet) once daily (or placebo)			X	X	X	X													
Vitamin C 3000mg (2 capsules) twice a day		X	X	X	X	X	X	X	X	X	X								
Vitamin D 3000IU (2 capsules) twice a day		X	X	X	X	X	X	X	X	X	X								
Zinc 50mg (2 capsules) twice a day		X	X	X	X	X	X	X	X	X	X								
Vitamin C 1500mg (1 capsule) twice a day												X	X	X	X	X			
Vitamin D 1500IU (1 capsule) twice a day												X	X	X	X	X			
Zinc 25mg (1 capsule) twice a day												X	X	X	X	X			
Ask about AE and SAE				X				X			X				X		X	X	X
Vitals in-clinic f																	X	X	X
Physical exam																	X	X	X
EKG in-clinic																	X	X	X
Swabs for RT-PCR				X		X		X							X		X		X
Bloodwork g																	X	X	X
Review list of prior and concomitant medications		X	X	X	X	X	X	X	X	X	X	X	X	X	X	X	X	X	X
SARS-CoV-2 Antibody test (optional, +4 days)																	X		
Blood Hydroxychloroquine level (optional)																	X		

- a. To include hydroxychloroquine 200mg tablets (#20), azithromycin 250mg tablets (#6), vitamin C 750mg capsules (#80), vitamin D 750IU capsules (#80), zinc 12.5mg capsules (#80)
- b. To include EKG (worn continuously), pulse oximeter, and thermometer
- c. If Subject is a woman of childbearing potential
- d. To remind them to collect swabs for RT-PCT, ask about AE/SAE, ask about symptoms, and answer any questions

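### The Day 1 timing sentence implies a second daily azithromycin intake that the dose tables, the Schedule of Events and Section 7 do not contain

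*Combined protocol and SAP*

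**What the plan says.** Two places in Section 3 (Study Procedures) give intake times in prose.

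- Under prescription of treatment drugs, the protocol has the drugs taken after eating in the morning. It then adds "Vitamins will be taken with lunch and dinner, and then the evening dose of drugs will be right before bed". The evening drug is not named.
- Under the Day 1 dose table, it says "Hydroxychloroquine and azithromycin will be taken early in the morning with breakfast and right before bed", followed by "Vitamins and Zinc will be taken with lunch and dinner".

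The parts of the protocol that state an amount or a frequency are these.

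- The Day 1 table has the row "Azithromycin (or Placebo) 500mg" in the AM column, with a dash in the PM column. The tables for Days 2 to 5 have "Azithromycin (or Placebo) 250mg" in the AM column, again with a dash under PM.
- The Schedule of Events (Section 6) has "Azithromycin 500mg (2 tablets) once daily (or placebo") for Day 1 and a one-tablet, once-daily row for Days 2 to 5. Its footnote a lists "azithromycin 250mg tablets (#6") among the items supplied.
- Section 7 (Dosage of Investigational Product) gives the azithromycin frequency as daily and the hydroxychloroquine frequency as BID. The matching placebo is two tablets on Day 1 and one on each of Days 2 to 5.

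For the supplements, the Section 3 tables show one AM and one PM entry, for example "Vitamin C 1500mg 1500mg" on Day 1.

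**The concern.** The Day 1 sentence has one verb, two drugs and two times of day. Nothing in it confines bedtime to hydroxychloroquine. The general rule earlier in Section 3 does not settle the matter, because it speaks of an evening dose without saying of which drug. Taken as written, the prose has azithromycin twice a day, while the tables, the Schedule and Section 7 have it once.

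Subjects take the drugs at home. The Day 1 video call is the only one before Day 3 and the only one that lists medication dosing in general. A misreading could therefore run for two days before the next scheduled contact. The regimen is followed by daily EKG on Days 1 to 10, and Appendix 4 has subject stopping criteria based on the QT interval, so the number of intakes per day bears on safety. The sentence covers placebo as well, so either arm could depart from the described regimen.

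There is also a smaller labelling point. The prose places the vitamins (and, under Day 1, zinc) at the midday and evening meals. The tables put the same products under AM and PM, the same column headings used for the two drugs.

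**Working it through.** No sample-size or power figure depends on this point. The check is a tablet count.

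**Inputs.** Azithromycin 500 mg on Day 1 and 250 mg on each of Days 2 to 5 (Section 3, Section 7, Schedule of Events); tablet strength 250 mg and 6 tablets dispensed (Schedule of Events, footnote a); two intake times (the Day 1 timing sentence).

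**1. Reproduce the supply on the once-daily reading.**
500/250 + 4 × (250/250) = 2 + 4 = 6 tablets, and 6 × 250 = 1500 mg. This equals the stated supply.

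The other counts in footnote a can be reproduced from the Section 3 tables in the same way:
- Hydroxychloroquine: 10 days × 2 = 20 tablets (stated 20).
- Vitamin C: 10 × 2 × (1500/750) + 20 × 2 × (750/750) = 40 + 40 = 80 capsules (stated 80). Vitamin D and zinc give 80 by the same calculation.

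**2. Take the table dose at both stated times.**
The full course would need 2 × (2 + 4) = 12 tablets, or 3000 mg. That is 6 tablets more than are dispensed. With 6 tablets in the kit:

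| Day | Tablets used | mg that day | Table dose, mg | Tablets left |
|---|---|---|---|---|
| 1 | 4 | 1000 | 500 | 2 |
| 2 | 2 | 500 | 250 | 0 |
| 3–5 | none available | 0 | 250 per day | 0 |

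The supply ends on Day 2, before the Day 3 call. Intake on Days 1 and 2 is twice the table dose. The total is 1000 + 500 = 1500 mg, the same as on the once-daily reading.

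**3. Split the daily amount over the two times.**
Day 1: 500/2 = 250 mg, one tablet per intake. Days 2 to 5: 250/2 = 125 mg, half a tablet per intake. The total stays at 1500 mg. No part of the protocol mentions half-tablets.

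**4. Supplements.**
The prose gives two meal times, and the Section 3 tables give two entries per day. The timing sentences state no amount. The difference is therefore only between the AM and PM labels and the meals named in the prose.

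**The case against.** The strongest reply is that this is one loosely drafted sentence set against a consistent body of text. Every statement that carries an amount or a frequency for azithromycin agrees: the prescription paragraph, the five daily tables, the Schedule, Section 7 and the tablet count. A reader can match breakfast and bedtime to the AM and PM columns and take the dash under PM to mean that nothing is due at bedtime. Further calls follow on Days 3, 5, 7, 10 and 14, and subjects can ask questions. The kit also caps exposure.

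Most of this stands. It limits how likely a misreading is, and it rules out calling the sentence a stated second dose. It does not remove the contradiction, because neither timing passage says that azithromycin is excluded from the bedtime intake. The Day 3 call comes too late on the literal reading, and its listed topics include no tablet count or check of azithromycin intake.

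Two further limits are fair. The instructions given to subjects are not in the documents, so it is an inference that they would repeat this sentence. The risk list in Section 13.1 names QT prolongation under hydroxychloroquine and not under azithromycin, so the safety argument rests on the QT stopping criteria for the regimen as a whole.

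On the supplements, the reply is nearly complete. The meal times are printed next to the table, the number of intakes is the same, and no passage says that separating supplements from the drugs matters.

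**Conclusion.** The protocol contradicts itself on how many times a day azithromycin or its placebo is taken. The prose in Section 3 implies two intakes. The Day 1 to 5 tables, the Schedule of Events and Section 7 give one. If the table dose were taken at both times, daily intake on Days 1 and 2 would be twice the table dose, and none would remain for Days 3 to 5.

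This size rests on three assumptions: the subject takes the full table dose each time, there is no resupply (none is described), and the placebo kit matches the active kit of 6 tablets. The last is consistent with the placebo tablet numbers in Section 7, but a dispensed placebo count is not given.

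A reader might infer more than the documents support:
- **That the protocol states a doubled dose.** The sentence gives no amount; the second dose is only implied.
- **That total azithromycin exposure doubles to 3000 mg.** Only 6 tablets are supplied, so the literal reading compresses 1500 mg into two days.
- **That subjects will in fact be misdosed.** Without the subject instructions and labels, this cannot be established.
- **That the tables have supplements taken together with the drugs.** The tables name no meal or clock time, so this is a labelling matter.

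The point is worth correcting because it concerns a self-administered regimen with QT stopping criteria. It does not affect the sample size, the endpoints or the planned analysis.

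**What to change.** Reconcile the two timing passages in Section 3 (under prescription of treatment drugs and under Day 1) with the Section 3 dose tables, the Schedule of Events and Section 7. After the change, each product should have one stated number of intakes per day and one stated time for each intake, worded identically for both arms. Any intake described as an evening dose should name the product it refers to. The column labels for the vitamins and zinc should agree with whatever times are kept in the prose. Subject instructions should then carry the same wording.

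The sponsor decides which text is correct; this review does not. The cost is a wording amendment. The dispensed tablet number should be checked against the text that is kept, since the present 6 tablets match only a total of 1500 mg over the course.

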**Duration of Subject Participation (Study Visits)**

Subjects will be given the opportunity once diagnosis has been made via RT-PCR testing to participate. They may be recruited through the ProgenaBiome website, through a questionnaire. They may also be recruited through [www.clinicaltrials.gov](http://www.clinicaltrials.gov). Subjects may be referred by healthcare facilities. Subjects may also self-refer as well. All potential Subjects will be called during the recruitment process for screening assessments. The first step of this will be to obtain informed consent electronically, via the EDC. We will attempt to connect with these Subjects via Zoom/telemedicine. The validity of the test used to diagnose will be verified through medical records. (The diagnosis will be made by the Subject's evaluating physician or evaluation testing center, as part of the standard of care when infection is suspected). Following successful screening, Subjects will be randomized into the Arm 1 (treatment) or Arm 2 (placebo). At this time the associated treatment regimen will be prescribed and shipped to the Subject's home, along with home health equipment (MoMe Kardia II, thermometer, pulse oximeter and pregnancy test). Subjects will take azithromycin for 5 days, and hydroxychloroquine for 10 days, along with vitamin C, vitamin D, and zinc. Starting at Day 11 Subjects will discontinue hydroxychloroquine and reduce the doses of vitamin C, vitamin D, and zinc. The vitamin C, D, and zinc will be taken an additional 20 days at the reduced dose. Subjects will use the home EKG to transmit heart function information to the Study Team to be read by a board-certified cardiologist prior to dosing. The EKG will then be used daily for 10 days and results transmitted to the study team. Subjects will use a home pulse oximeter to monitor oxygen saturation and photographically report these values to the study team via the EDC. Subjects will track their symptoms using a daily diary (provided). Subjects will collect nasal or oropharyngeal swabs on Days 3, 5, 7, 14, and Month 1 and Month 3 for RT-PCR testing. Once Subjects have tested negative following treatment with HAZDpaC, Subjects will present to the clinic at 1, 2, and 3 months post-treatment for viral testing via RT-PCR. Alternatively, these visits may be conducted via videoconference and the subjects may collect these samples at home. At these visits blood will be drawn, a physical exam performed, and vital signs measured (optional). At the month 3 visit a pregnancy test will be given if applicable. Should Subject remain symptomatic at 2 weeks, or return to a positive state at any time during the trial they will be referred to their PCP by a phone call directly from the PI to the PCP. If at any time during the treatment phase or subsequent follow up Subject expresses and demonstrates a worsening or persistence of symptoms, they will be cared for according to standard of care or referred to their primary care provider, according to patient preference. The PI will discuss the case directly with that primary care provider. Subjects will continue to be followed for the remainder of the trial, and documentation of any additional treatments and Subject outcomes will be collected.

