- Temperature

- d. Subject will take prescribed regimen

Drug	AM Dose	PM Dose
Hydroxychloroquine (or Placebo)	200mg	200mg
Vitamin C	1500mg	1500mg
Vitamin D	1500IU	1500IU
Zinc	25mg	25mg

- o Day 11-Day 13

- a. Subject will complete AM/PM diaries

- b. Subject will take prescribed regimen

Drug	AM Dose	PM Dose
Vitamin C	750mg	750mg
Vitamin D	750IU	750IU
Zinc	12.5mg	12.5mg

- o Day 14

- a. Subject will be called

- Remind them to collect nasal or oropharyngeal swab
- Ask about AE/SAE
- Symptom resolution or progression
- Answer any questions the Subject may have

- b. Subject will collect nasal or oropharyngeal swab

- c. Subject will complete AM/PM diaries

- d. Subject will take prescribed regimen

Drug	AM Dose	PM Dose
Vitamin C	750mg	750mg

Vitamin D	750IU	750IU
Zinc	12.5mg	12.5mg

- Day 15-30
  - a. Subject will complete AM/PM diaries
  - b. Subject will take prescribed regimen

Drug	AM Dose	PM Dose
Vitamin C	750mg	750mg
Vitamin D	750IU	750IU
Zinc	12.5mg	12.5mg

- Follow-Up Period (These visits can be conducted via videoconference or in person)
  - Month 1 (outpatient only AFTER negative test)
    - a. Vital signs (BP, HR, RR, oxygen saturation, temperature)
    - b. Assessment for AE and SAE
    - c. EKG (Optional)
    - d. Physical exam (Optional)
    - e. Blood draw for CBC/Complete metabolic panel/C-Reactive Protein/Blood hydroxychloroquine levels/SARS-CoV Antibody test (All optional)
      - Blood HQ levels will remain blinded from all but unblinded coordinator
    - f. Update list of prior and concomitant medications
    - g. Study team will collect nasal or oropharyngeal swab (If patient elects to refrain from this in-person visit they will collect this at home)
  - Month 2 (outpatient)
    - a. Vital signs (BP, HR, RR, oxygen saturation, temperature)
    - b. Assessment for AE and SAE
    - c. EKG (Optional)
    - d. Physical exam (Optional)
    - e. Blood draw for CBC/Complete metabolic panel/C-Reactive Protein (Optional)
    - f. Update list of prior and concomitant medications
  - Month 3 (outpatient)
    - a. Vital signs (BP, HR, RR, oxygen saturation, temperature)
    - b. Assessment for AE and SAE
    - c. EKG (Optional)
    - d. Physical exam (Optional)
    - e. Blood draw for CBC/Complete metabolic panel/C-Reactive Protein (Optional)
    - f. Update list of prior and concomitant medications

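### The protocol contradicts itself on whether Month 1-3 assessments need a prior negative test, and one reading makes late data depend on the primary endpoint

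*Combined protocol and SAP*

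**What the plan says.** Two places state a condition. In Section 3 (Study Procedures, Follow-Up Period) the Month 1 visit is headed "Month 1 (outpatient only AFTER negative test". In the synopsis, under Duration of Subject Participation, the condition covers all three visits: "Once Subjects have tested negative following treatment with HAZDpaC, Subjects will present to the clinic at 1, 2, and 3 months post-treatment". HAZDpaC is the synopsis's name for the active regimen.

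Other text is unconditional or points the other way:

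- Section 3 heads the next visit only "Month 2 (outpatient", with no mention of a negative test, and Month 3 is written the same way.
- The synopsis lists the swabs without a condition: "Subjects will collect nasal or oropharyngeal swabs on Days 3, 5, 7, 14, and Month 1 and Month 3 for RT-PCR testing".
- After describing subjects who stay symptomatic, worsen or return to positive, the synopsis says: "Subjects will continue to be followed for the remainder of the trial, and documentation of any additional treatments and Subject outcomes will be collected".
- The Schedule of Events marks adverse event questions at Months 1, 2 and 3 and swabs at Months 1 and 3, with no footnote about a negative test.
- The synopsis sets adverse event and serious adverse event monitoring at 12 weeks. Sections 11.6 and 11.7 run reporting from consent to the end-of-study visit.

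Both places also allow remote visits: "Follow-Up Period (These visits can be conducted via videoconference or in person" in Section 3, and "Alternatively, these visits may be conducted via videoconference and the subjects may collect these samples at home" in the synopsis.

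**The concern.** The primary endpoint in the synopsis and Section 2 is the number of days from diagnosis to recovery by RT-PCR. A rule that admits subjects to late visits only once they have tested negative would select attendance on that same outcome. The subjects not assessed would be those who had not cleared the virus, and their number could differ by arm if the drugs affect clearance. Section 15 gives no rule for missing or censored PCR results and leaves further detail to a statistical analysis plan still to be written.

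Safety is also touched. After Day 14 the scheduled adverse event questions fall at Months 1, 2 and 3. The diary, which Appendix 3 says also asks about adverse events, stops at Day 30. Section 1 gives the half-life of hydroxychloroquine as 20-80 days, so the later enquiries are not a formality.

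**Working it through.** **Step 1. Set the passages side by side.**

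| Place | Visits covered | Negative test required? |
|---|---|---|
| Section 3, Month 1 heading | Month 1 | Yes, for the visit or for attending in person |
| Section 3, Month 2 and 3 headings | Months 2, 3 | Not stated |
| Synopsis, clinic-visit sentence | Months 1, 2, 3 | Yes, for presenting to the clinic |
| Synopsis, swab list | Months 1, 3 | No |
| Synopsis, continued follow-up | Rest of trial | No |
| Schedule of Events | Months 1, 2, 3 | No |
| Synopsis, adverse event monitoring | 12 weeks | No |

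No entry says what a subject who has never tested negative does at Months 1, 2 and 3.

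**Step 2. Ask whether such a subject could qualify under the literal reading.** Scheduled swabs fall on Days 3, 5, 7 and 14, then Month 1 and Month 3. None falls between Day 14 and Month 1. For a subject with no negative result by Day 14, the next scheduled swab belongs to the Month 1 visit, which is the visit that requires the negative result. Only a test outside the study schedule could break the circle.

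**Step 3. List what would be lost under that reading.**

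- PCR: the Month 1 and Month 3 swabs.
- Adverse events: the Month 1, 2 and 3 questions. Diary enquiry continues to Day 30, and no scheduled enquiry remains after it.
- Vital signs: the Month 1, 2 and 3 measurements. The 1- and 2-month values belong to a secondary endpoint in Section 2. This part is weaker, because the synopsis and the Schedule footnote mark these vital signs as optional, while Section 3 does not.
- EKG: not counted. Section 3 makes the Month 1-3 EKG optional for everyone.

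The Month 1 losses rest on Section 3 and the synopsis together. Those at Months 2 and 3 rest on the synopsis sentence alone.

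**Step 4. Size.** The denominator is the 600 of Section 15. Its formula reproduces: log 0.050 / log 0.995 = 597.647, rounded to 600. It is used here only as a head count. The documents give no share q of subjects without a negative swab by Day 14, so q is an assumption. Number affected = 600 x q:

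| Assumed q | Affected, literal reading | Lost to the rule, in-person-only reading |
|---|---|---|
| 5% | 30 | 0 |
| 10% | 60 | 0 |
| 20% | 120 | 0 |
| 30% | 180 | 0 |

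**The case against.** The strongest reply is that the condition only keeps infectious people out of the clinic. The synopsis sentence governs presenting to the clinic, and the next sentence offers video and home sampling. In Section 3 the condition can qualify the word outpatient, under a heading that allows either mode. Section 3 also requires isolation and self-quarantine, which fits. The circularity in Step 2 supports this reading too, since a sponsor is unlikely to have meant a rule that its own schedule cannot satisfy.

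This is a fair reading and may be the intended one. It does not close the matter. The visits that the synopsis says may be held by video are the ones it has just made conditional, so the sentence can be taken to change their mode and not who receives them. In Section 3 the home swab is for a patient who chooses not to attend in person; it is not assigned to subjects who are still positive. The continued-follow-up sentence promises treatments and outcomes but names no swab, vital signs or adverse event questions at fixed months. The unconditional passages contradict the condition without explaining it.

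Three stronger inferences are tempting, and the documents do not support them:

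- That late data will be missing. This follows from only one of two available readings, and several passages oppose it.
- That a true treatment difference would disappear. With an assumed 300 per arm and assumed 10% and 20% without a negative test, 300 x 0.10 = 30 and 300 x 0.20 = 60 subjects would be absent, and a Month 1 comparison among attenders could show little beyond relapses. But both rates are invented, and that comparison is a cross-section at Month 1. The primary endpoint is time to recovery, which the swabs on Days 3, 5, 7 and 14 also inform. A never-negative subject is known to be unrecovered at Day 14 and could be censored, so early differences between arms would remain.
- That follow-up is meant for the active arm only, because the synopsis names HAZDpaC. The trial is double-blind, so blinded staff could not apply such a rule. The wording is a slip, but one that leaves placebo subjects without a stated trigger.

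**Conclusion.** The concern holds as an internal contradiction. The protocol both requires and does not require a negative test before the Month 1-3 assessments, and it is silent on subjects who never test negative. Under the in-person-only reading the rule costs no data. Under the literal reading, later PCR and scheduled adverse event assessments, and vital signs where taken, would be absent for subjects with no negative swab by Day 14, and the absence would depend on the primary endpoint. The range of 30 to 180 of 600 rests wholly on the assumed 5% to 30% and on the literal reading being applied to everyone. It describes exposure to the problem and is not a forecast of loss. The point deserves correction because staff could in good faith apply either reading, and Section 15 has no missing-data rule to contain the consequence.

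**What to change.** Reconcile the synopsis (Duration of Subject Participation), the Section 3 Follow-Up Period and the Schedule of Events so that all three say the following:

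- The Month 1, 2 and 3 assessments are due for every randomised subject in both arms, whatever the PCR status, with swabs at the visits where the Schedule has them. The synopsis sentence on viral testing also covers month 2, but Section 3 and the Schedule have no Month 2 swab, so this can be settled in the same edit.
- Any negative-test condition applies only to attending in person. Subjects still positive use the video visit and home swab already provided for.
- The words tying the negative test to treatment with HAZDpaC are deleted.
- One time anchor is stated for these visits. The synopsis counts months post-treatment; if another anchor is meant, the change should be made openly.

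The cost is mainly wording, plus a few more remote visits. One limit should be acknowledged: Section 3 lists blood pressure among the follow-up vital signs, but the home monitoring equipment is an EKG device, a pulse oximeter and a thermometer, so blood pressure may be unavailable at remote visits.
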